9.2 Determination of Sample Size

In total, a maximum of approximately one hundred thirty-four (134) subjects with a MI and resulting ischemic left ventricular dysfunction meeting all inclusion and no exclusion criteria will be enrolled. The first fourteen (14) subjects (7 Recent MI and 7 Chronic MI) will receive CAP-1002 open-label and will be designated as the Safety Cohort. The approximate maximums of one hundred three (103) subjects in the Primary Randomized Cohort (51-52 Recent MI and 51-52 Chronic MI) and the up to 17 subjects in the Exploratory Randomized Cohort will begin to enroll only after DSMB review of the Safety Cohort data and recommendation to proceed. These approximately 120 subjects in the Primary Randomized Cohort and Exploratory Randomized Cohort will be independently randomized in a double-blind fashion to receive either CAP-1002 or placebo in a 2:1 ratio, favoring CAP-1002 to achieve approximately up to 93 subjects with complete 12 month data in the Randomized Cohort. A balancing algorithm will be used to ensure site-specific balancing to the 2:1 allocation after stratifying for prior MI.

The Safety Cohort was evaluated once all subjects reached the primary safety endpoint assessed at the 1 month visit. With n=14, if no significant safety events are observed, the one-sided 95% upper bound for the true rate of significant events would be < 20%. The DSMB conducted a review of the Safety Cohort data and made a recommendation to proceed with randomization of the next 120 subjects. Efficacy and safety will be assessed at all post-screening visits, although

MRI testing will only be completed at 6 and 12 months; the 12 month visit is the primary efficacy endpoint.

Historical Data

The CADUCEUS and ALLSTAR Safety Cohort data provide some background for planning sample size to test for efficacy. The efficacy endpoints in the CADUCEUS study and in the ALLSTAR Safety Cohort included the relative change in the Month 6 and 12 outcomes relative to baseline as judged by MRI assessment of infarct size (measured in %). Assumptions used for power calculations are summarized below in [Table 4](#) with the relative change displayed as a percent improvement from baseline. The ALLSTAR Safety Cohort was used for the assumed means and SDs and CADUCEUS was used for the treatment effect in Chronic MI patients relative to Recent MI.

Table 4. Sample Size Assumptions

| | Month 6 | | Month 12 | |
|------------------|---------|-------|----------|-------|
| | Mean | SD | Mean | SD |
| CAP-1002 Recent | 6.20 | 10.00 | 14.70 | 10.00 |
| CAP-1002 Chronic | 3.10 | 10.00 | 7.35 | 10.00 |
| Placebo | 0.00 | 10.00 | 0.00 | 10.00 |

Power calculations using Monte Carlo simulation indicated that, under these assumptions, the trial will have more than 90% power to be declared successful with a total sample size of 100.

Primary Randomized Cohort

The Primary Randomized Cohort is designed to assess the efficacy of the study agent as well as further evaluate the safety profile of CAP-1002. Up to 103 subjects will be enrolled in the Primary Randomized Cohort. This maximum sample size is based on the Recent and Chronic MI strata being analyzed independently with a treatment effect of 15% at Month 12 for each strata, a pooled standard deviation of 10%, a minimum power of 80%, and a significance level (alpha) of 0.05.

Exploratory Randomized Cohort

The Exploratory Randomized Cohort sample size of up to 17 subjects was estimated based on DSA results observed in the Safety Cohort, where approximately 14% of the screened subjects had pre-formed antibodies to all available donors. That is, assuming a 14% rate of pre-formed DSAs, approximately 120 subjects would be screened to achieve enrollment of 103 in the matched Primary Randomized Cohort, thus yielding up to 17 subjects enrolled in the Exploratory Randomized Cohort. Enrollment into the Exploratory Randomized Cohort is capped at n=17, with no pre-specified limit for subject counts in the Recent and Chronic stratum. Enrollment in the study will be complete when the Primary Randomized Cohort is fully enrolled, regardless of whether the Exploratory Randomized Cohort has enrolled.

9.3 Analysis Populations

Treated subjects (those who have undergone infusion) from all Cohorts will be followed for 12

months. Subjects will have study visits at 2 weeks, 1, 3, 6, and 12 months following infusion. Subjects enrolled in the Safety Cohort will also have a 2 month study visit.

The analysis population for assessing safety will consist of all subjects in a given Cohort (Safety, Randomized) who received an infusion of either CAP-1002 or placebo. The primary analysis population for assessing efficacy will consist of all subjects in the safety population from Primary Randomized Cohort (Primary Modified Intent-to-Treat (mITT) Population) who had a baseline observation and at least one post-baseline observation. The Safety Cohort subjects will be summarized and analyzed distinctly from the Randomized Cohort due to the unblinded nature of the treatment assignment. Similarly, the Exploratory Randomized Cohort of mismatched subjects will also be summarized distinctly from the Primary Randomized Cohort. Details on additional analysis populations will be addressed in the SAP.

9.4 Demographics and Baseline Characteristics

Demographics and baseline characteristics of all accrued subjects such as race, ethnicity, sex, and age will be summarized and reported. The gender and minority distributions are expected to reflect a highly multicultural infarct subject population. There are no particular recruitment strategies for women or minorities.

9.5 Primary Endpoint(s)

9.5.1 Primary Safety Endpoint(s)

Medical Dictionary for Regulatory Activities (MedDRA) will be used for this study to code adverse events.

The primary safety endpoint is the proportion of subjects experiencing any of the following adjudicated events within one month following intracoronary infusion:

1. Acute myocarditis possibly attributable to CAP-1002 or placebo, diagnosed with consideration of clinical context, with or without a clinically indicated endomyocardial biopsy. In order to be considered related to CAP-1002 or placebo, humoral or cellular immune reaction specific to CAP-1002 must also be documented for subjects treated with CAP-1002, or a temporal relationship with IP administration must exist for subjects administered placebo.
2. Death due to ventricular tachycardia or ventricular fibrillation defined as occurring with ECG documentation of these arrhythmias during ambulatory ECG monitoring in an outpatient setting, or during routine ECG monitoring while hospitalized.
3. Sudden unexpected death defined as occurring within one hour of symptom onset, or unwitnessed death in a person previously observed to be well within the preceding 24 hours without an identified cause.
4. Major adverse cardiac event (MACE), defined as the composite incidence of death, non-fatal recurrent MI, hospitalization for heart failure, emergency room treatment for heart failure (NT-proBNP >450 pg/mL or BNP >100 pg/ml, with treatment including intravenous diuretic administration), left ventricular assist device (LVAD) placement or heart transplant. Peri-infusion MI will be defined as presence of troponin or CK-MB levels > 5 times the upper reference limit during the 24 hours following infusion. These elevations must be

accompanied by symptoms of ischemia >20 minutes in duration and ECG changes indicative of new ischemia (new ST-T changes or new left bundle branch block), development of pathological Q waves on the ECG, imaging evidence of new loss of viable myocardium, or new regional wall motion abnormality.

Point estimates and two-sided 95% confidence intervals for the proportion of subjects who experience any of the four events will be presented. Similarly, each of the four endpoints will be summarized separately with point estimates and two-sided 95% confidence intervals for the proportion of subjects who experience each event within the first month post-infusion. Also, two-sided 95% confidence intervals will be constructed for the difference between CAP-1002 and placebo and a two-sided Fisher Exact test will be used to compare the treatments for the Safety Analysis Set.

9.5.2 Primary Efficacy

The primary efficacy objective is to determine if the administration of CAP-1002 by intracoronary infusion may result in structural cardiac benefits for subjects with ischemic left ventricular dysfunction and a previous MI as measured by the percent change from baseline in the MRI assessment of infarct size as a percent of left ventricular mass at 12 months post administration. Baseline assessments are conducted during the “Screening” visit, prior to the administration of CAP-1002 or placebo.

The primary efficacy hypothesis is that CAP-1002 is superior to placebo in reducing infarct size in either all subjects combined (“full group”) or in subjects with recent MI (“subgroup”). A closed testing procedure will be used so that strong control of type 1 error is maintained. Specifically, the following hypothesis sets will be tested:

$$1) \quad \begin{array}{lll} H_{0,s}: \mu_{c,s} - \mu_{p,s} = 0 & \text{or} & H_{0,f}: \mu_{c,f} - \mu_{p,f} = 0 \\ H_{a,s}: \mu_{c,s} - \mu_{p,s} < 0 & & H_{a,f}: \mu_{c,f} - \mu_{p,f} < 0 \end{array}$$

and

$$2) \quad \begin{array}{ll} H_{0,s} \cap H_{0,f}: \mu_{c,s} - \mu_{p,s} = 0 \text{ and } \mu_{c,f} - \mu_{p,f} = 0 \\ H_{a,s} \cap H_{a,f}: \mu_{c,s} - \mu_{p,s} < 0 \text{ or } \mu_{c,f} - \mu_{p,f} < 0 \end{array}$$

where s denotes the subgroup, f denotes the full group, $\mu_{c,s}$ and $\mu_{p,s}$ are mean percent changes in the CAP-1002 and placebo treatment groups, respectively, in the subgroup, and $\mu_{c,f}$ and $\mu_{p,f}$ are mean percent changes in the CAP-1002 and placebo treatment groups, respectively, in the full group.

Therefore, both the intersection null hypothesis ($H_{0,s} \cap H_{0,f}$) and either of the individual null hypotheses ($H_{0,s}$ or $H_{0,f}$) must be rejected at the (one-sided) 0.025 significance level for the trial to be declared a success. In other words, the null hypothesis of “no treatment effect in the full group and no treatment effect in the recent MI subgroup” must be rejected at the one-side 0.025 significance level, necessarily meaning that either the result is significant in the full group, in the recent MI subgroup, or both. The results of the tests of the individual hypotheses (also at the one-sided 0.025 significance level) determines which specific comparisons are significant.

The primary analysis will be a longitudinal mixed effects model. The response variable of percent change from baseline in infarct size as a percent of left ventricular mass will be modeled with the fixed categorical effects of treatment group and time (6 and 12 months), as well as a continuous fixed covariate of baseline infarct size. Intercept and subjects will be treated as random in this mixed effects model. The primary hypothesis will be tested using the estimate of treatment effect compared to placebo at 12 months. An additional test will compare the treatments at 6 months and will be considered secondary. Model results will be provided for fixed affects and estimates for each level of each affect. A mean profile plot will be presented to describe the treatment response over time.

The final primary efficacy analysis population will depend on the results of the adaptive design interim analysis. The final analysis will use the above model and the study result will depend on the result of a Dunnett intersection test p-value calculated from the final mixed model results similarly to the interim. The adaptive design interim analysis conducted on approximately 80 subjects with 6 month follow-up data in the Primary Randomized Cohort across the Recent MI and Chronic MI strata will determine whether the analysis will be based on the strata combined or the Recent MI strata alone. See the Adaptive Design IAP for details.

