specific to CAP-1002), death due to ventricular tachycardia or ventricular fibrillation, sudden unexpected death, or a major adverse cardiac event (MACE), defined as the composite incidence of death, non-fatal recurrent MI, hospitalization for heart failure, emergency room treatment for heart failure (NT-proBNP >450 pg/mL or BNP >100 pg/ml, with treatment including intravenous diuretic administration), left ventricular assist device (LVAD) placement or heart transplant within the first month post-infusion will be calculated.

Secondary Safety Endpoints: Descriptive analyses of all secondary safety endpoints will be performed using percentages, means, and ranges where appropriate. For incidence rates, two-sided 95% confidence intervals will be constructed for the differences between CAP-1002 and placebo and a two-sided Fisher Exact test will be used for between-treatment comparisons; the Wilcoxon-Mann-Whitney test will be used to compare distributions and ordinal outcomes between randomized treatments. There will be no adjustments for multiple safety assessments by the DSMB and at the interim analyses; a two-sided $p=0.05$ will be used to establish statistical significance.

Primary Efficacy Endpoint: The primary efficacy endpoint is the percent change from baseline in MRI assessment of infarct size as a percent of left ventricular mass 12 months after administration of treatment (either CAP-1002 or placebo). The primary efficacy hypothesis is that CAP-1002 is superior to placebo in reducing infarct size in either all subjects combined (“full group”) or in subjects with recent MI (“subgroup”). A closed testing procedure will be used so that strong control of type 1 error is maintained.

The primary analysis will be a longitudinal mixed effects model. The response variable of percent change from baseline in infarct size as a percent of left ventricular mass will be modeled with the fixed categorical effects of treatment group and time (6 and 12 months), as well as a continuous fixed covariate of baseline infarct size. Intercept and subjects will be treated as random in this mixed effects model. The primary hypothesis will be tested using the estimated treatment effect compared to placebo at 12 months. An additional test will compare the treatments at 6 months and will be considered secondary. Model results will be provided for fixed affects and estimates for each level of each affect.

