## 2. STUDY OBJECTIVES, TREATMENTS, AND ENDPOINTS

### 2.1 Objectives

#### 2.1.1 Primary Objectives

The primary safety objective is to test the null hypothesis that the incidence rate of the primary safety endpoint (a composite of peri-procedural clinical events) differs by no more than 0.20 between treatment groups in subjects with ischemic left ventricular (LV) dysfunction and a previous MI receiving CAP-1002 or placebo by intracoronary infusion.

The primary efficacy objective is to test the hypothesis that, in subjects with ischemic LV dysfunction and a previous MI, CAP-1002 by intracoronary infusion is superior to placebo in reducing infarct size, expressed as a percent of LV mass, 12 months after infusion, either in all subjects combined or in subjects with recent MI (<= 90 days before infusion).

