### **2.3.4 Primary Efficacy Endpoint**

The primary efficacy endpoint is the percent change from baseline in MRI assessment of infarct size as a percent of LV mass 12 months after IP administration.

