## 9. EFFICACY ANALYSIS

All efficacy parameters will be listed for the primary ITT population and summarized for the mITT population. The primary analysis of primary and secondary efficacy endpoints will be done using the primary mITT population. Secondary analyses may be done using the other analysis populations defined in [Section 6](#) or in subgroups defined in [Section 7.4](#). In addition, “last observation” analyses will be done for certain parameters for which some subjects’ final assessments were done too late to be included in the Month 12 analysis window.

Analyses of changes from baseline will be done using general linear models with baseline values as covariates. Analyses of the effect of treatment group, analysis window (e.g., baseline, Month 6, Month 12), and their interaction will be done using mixed effects linear regression, with subject as a random effect, analysis window, and treatment group as fixed effects, and baseline as a fixed-effect covariate. For “last observation” analyses, “time” as a continuous covariate will be substituted for analysis window. Study site may also be included as a random effect if there is evidence of correlation within study sites (per the interclass correlation coefficient from the unconditional model) and/or if doing so appreciably improves the model fit (e.g., per Akaike’s Information Criterion). Other covariates that may be considered include age (< 65 vs.  $\geq$  65 years), sex, race (African-American vs. other), baseline 6MWT, baseline LVESV, baseline NT-proBNP, and DSA (as an indicator variable). Residuals will be evaluated for substantial departure from normality and independent and constant variance and appropriate remedies (e.g., data transformations, detecting and assessing the influence of outliers, alternative analytical approaches) will be attempted when necessary. An unstructured covariance will be the default covariance structure but other structures (e.g., compound symmetry) may be used to evaluate sensitivity to the choice of structure or, if study site is included as a random effect, to achieve convergence.

Assuming missing observations are “missing at random” (MAR), i.e., the fact that they are missing is unrelated to the missing variable but can be related to another variable on which data have been collected, the maximum likelihood (ML) approach is able to handle subjects with

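### The primary model's listed fixed effects leave out treatment × visit, although separate 12- and 6-month tests are required, and the full-group model leaves out the Recent/Chronic MI stratum

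*Protocol*

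**What the plan says.** **Model.** Protocol 9.5.2 gives the fixed effects as "the fixed categorical effects of treatment group and time (6 and 12 months), as well as a continuous fixed covariate of baseline infarct size", with a random subject intercept. The Synopsis gives the same list.

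**Tests.** Protocol 9.5.2 continues: "The primary hypothesis will be tested using the estimate of treatment effect compared to placebo at 12 months", and then "An additional test will compare the treatments at 6 months and will be considered secondary". The Synopsis agrees: "The primary hypothesis will be tested using the estimated treatment effect compared to placebo at 12 months". The Dunnett intersection p-value is to be "calculated from the final mixed model results similarly to the interim". For details 9.5.2 refers to an Adaptive Design IAP, which is not among the documents.

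**Endpoint.** It is fixed at one visit. SAP 2.1.1 says "12 months after infusion, either in all subjects combined or in subjects with recent MI", and SAP 2.3.4 says "infarct size as a percent of LV mass 12 months after IP administration".

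**SAP model.** Section 9 assigns to mixed-effects regression "Analyses of the effect of treatment group, analysis window (e.g., baseline, Month 6, Month 12), and their interaction". The list that completes that sentence has subject as random, window and treatment as fixed, and baseline as covariate. The interaction is not in that list. The closed-test steps in section 9 take the full-group and subgroup p-values from LS-mean comparisons, without naming a visit or a model. Section 14 declares no deviations from the protocol's methods.

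**Stratum.** Protocol 5.2 and SAP 5 randomise 2:1 within Recent/Chronic MI. Neither document puts stratum in the full-group model, and it is not among the optional covariates named in SAP 9.

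**The concern.** A model with treatment and time main effects only forces one treatment difference on both visits. Fitted as listed, it would report the same number as the 12-month primary result and the 6-month secondary result, and that number would be an average over the two visits. The label would say Month 12 and the estimate would not.

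Fitting the interaction does not fully settle the matter. A treatment LS mean that is not tied to a visit is conventionally averaged over visits, so the closed-test p-values need a stated visit as well as the right model.

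The stratum issue is different in kind. Stratified allocation keeps the arms balanced on MI timing, so the effect estimate hardly depends on it. If the model leaves stratum out, any difference between strata goes into the residual variance and the reported standard error exceeds the true one.

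**Working it through.** **Inputs.** Table 4 (Protocol 9.2; Table 1 in SAP 4) gives improvements of 6.20 and 14.70 (Recent) and 3.10 and 7.35 (Chronic) at Months 6 and 12, placebo 0, SD 10 throughout. Protocol 3.1 plans 93 completers at 2:1, so 62 v 31, split here as Recent 31 v 16 and Chronic 31 v 15. The one-sided level is 0.025 (Protocol 9.5.2). Assumptions: complete data, equal SDs, no baseline covariate, and within-subject correlation ρ from 0.3 to 0.9, since the documents give none.

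**The plan's own figure.** At N = 100 and 2:1, two-sample power is 99.9% for 11.025 in the full group and 99.8% for 14.70 in 50 Recent subjects. The stated power of more than 90% is met.

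**What each model targets under Table 4.**
- Full group, Month 6: (6.20 + 3.10)/2 = 4.65. Month 12: (14.70 + 7.35)/2 = 11.025.
- Listed model, full group: (4.65 + 11.025)/2 = 7.84, which is 29% below 11.03.
- Listed model, Recent: (6.20 + 14.70)/2 = 10.45, which is 29% below 14.70.

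A mixed-model fit to one simulated data set (n = 3,000, ρ = 0.5, random intercept, baseline covariate) confirms this. The additive coefficient is 8.26. The interaction model gives 5.33 at Month 6 and 11.19 at Month 12, whose mean is 8.26.

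**Closed test as in SAP 9** (20,000 simulated trials per setting, % declared successful):

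| Scenario | Contrast | ρ 0.3 | 0.5 | 0.7 | 0.9 |
|---|---|---|---|---|---|
| Table 4 effects | 6/12 average | 99.4 | 98.7 | 97.8 | 96.0 |
| Table 4 effects | Month 12 | 99.9 | 99.9 | 99.9 | 99.9 |
| Table 4 effect at Month 6, none at Month 12 | 6/12 average | 27.7 | 24.9 | 23.0 | 21.0 |
| Table 4 effect at Month 6, none at Month 12 | Month 12 | 2.7 | 2.7 | 2.9 | 3.0 |

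Under the complete null both contrasts succeed in 2.8 to 3.1% of trials, so about 3% is the baseline for this test.

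**Stratum, full-group Month 12 estimate.** The design factor is √(1/62 + 1/31) = 0.220, so the true SD is 10 × 0.220 = 2.20 (simulated 2.19 to 2.20, with or without stratum).

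Without stratum, the residual variance is about 100 + (2/3)(D_c/2)² + (1/3)(D_p/2)². D_c and D_p are the Recent-minus-Chronic differences in mean on CAP-1002 and on placebo, with D_c = D_p + 7.35. Under Table 4 this is 100 + (2/3)(3.675)² = 109.0, and √109.0 × 0.220 = 2.30 (simulated 2.29).

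With stratum, only the unequal treatment effect remains in the residual: 7.35²/(1/31 + 1/16 + 1/31 + 1/15) = 278.9. The residual variance is (90 × 100 + 278.9)/90 = 103.1, and √103.1 × 0.220 = 2.23 whatever D_p is.

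| Placebo Recent − Chronic (D_p) | Reported SE without stratum | With stratum | Excess |
|---|---|---|---|
| 0 (Table 4) | 2.29 | 2.23 | 3% |
| +5 (assumed) | 2.48 | 2.23 | 11% |
| +10 (assumed) | 2.77 | 2.23 | 24% |
| −5 (assumed) | 2.23 | 2.23 | 0% |
| −10 (assumed) | 2.30 | 2.23 | 3% |

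**The case against.** The strongest reply is that the interaction is already planned. Protocol 9.1 leaves the pre-specified analyses to the SAP, and SAP 9 names the interaction. The clause that follows can be read as saying only which factors are random and which are fixed. The additive model also contradicts the two sentences after it in Protocol 9.5.2, and the endpoint is 12 months everywhere. This largely stands: the intent is recoverable, and SAP section 14 is not wrong if the interaction merely implements the two required tests.

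A reader might infer that the plan as it stands would declare a 12-month success on a vanished early effect in 21 to 28% of trials. The documents do not support that. The figure needs a literal fit of the protocol list, against the SAP's naming of the interaction. It also needs an effect confined to Month 6, whereas Table 4 has the effect more than doubling from Month 6 to Month 12. It illustrates what the missing term would do and is not a risk of the analysis the SAP intends.

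SAP 9 also assigns analyses of change from baseline to general linear models, and one of these fitted at Month 12 would give a visit-specific contrast. That is a second candidate for the primary p-values, while Protocol 9.5.2 takes them from the mixed model. It is a further reason to name the model.

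On stratum, it is fair to say that the test is conservative, that the loss under Table 4 is small, that the SAP's covariate list is open-ended, and that Recent MI is tested in its own right. None of this is a reason to leave a randomisation factor to discretion when including it costs one degree of freedom. A reader might also infer a biased effect or inflated type I error from the omission. The calculations show neither.

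**Conclusion.** The point holds in two limited parts.

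1. The fixed-effect lists in the Synopsis, Protocol 9.5.2 and SAP 9 do not match the tests they are meant to deliver, and the closed-test steps state neither visit nor model for the two p-values. The intended Month 12 analysis is very probably right, and stated power is unaffected: at least 96% even under the literal list, given the ρ values assumed. What needs repair is the wording of the test that decides trial success. Whether the Adaptive Design IAP already settles it cannot be checked here.

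2. Omitting stratum from the full-group model leaves the estimate and its true SD (about 2.2) essentially unchanged. The reported SE is about 3% too large under Table 4. It is 11% or 24% too large if Recent placebo subjects improve 5 or 10 points more than Chronic, and 0 to 3% too large if the difference runs the other way. Those placebo differences are assumptions; Table 4 has one placebo mean for both strata. Adding the term is a nearly free gain in precision.

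**What to change.** - Add treatment × visit to the fixed effects listed in the Synopsis, Protocol 9.5.2 and SAP 9.
- In the closed-test steps of SAP 9, define the full-group and subgroup p-values as one-sided Month 12 treatment LS-mean contrasts from that mixed model.
- Add Recent/Chronic MI as a fixed effect in the full-group model and state which definition applies. SAP 3 defines the strata relative to randomisation, while SAP 7.4 reclassifies wrongly stratified subjects by time from MI to infusion. The SAP 7.4 classification, already used for the primary analysis, could serve, with the as-randomised stratum as a sensitivity analysis.
- Record the stratum term in SAP section 14.

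The cost is wording in the protocol and SAP, plus one degree of freedom for each term. Data collection and sample size do not change.
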